6.3 Dose modification for TLS and other toxicities

Venetoclax-associated tumor lysis syndrome (TLS) is predominantly seen in patients with CLL with high tumor burden. The risk of TLS in MDS is considered small. Additionally, limiting the white blood cell (WBC) as implemented by the inclusion criteria will further mitigate TLS risk.

Additional safety and efficacy data are described in more detail in the current version of the venetoclax Investigator's Brochure.

For patients who have had a dosing interruption lasting more than 2 weeks, TLS risk should be reassessed to determine if restarting at a reduced dose is necessary (e.g., all or some levels of the dose; see Table 3).

Table 3: Dose modification for TLS and other toxicities

Dose at interruption (mg)	Dose at restart (mg*)
400	300
300	200
200	100
100	50
50	20
20	10

* The modified dose should be continued for 1 cycle before increasing the dose.

6.4 Prohibited Medications and Therapy

The Following Medications and Therapy are not allowed during the study:

- Strong cytochrome P450 3A (CYP3A) inducers (consider alternative treatments with less CYP3A induction)
- Grapefruit, grapefruit products, Seville oranges (including marmalade containing Seville oranges) and star fruit (carambola) 3 days before starting study drug in each cycle.

Subjects must be consented for the study prior to discontinuing any prohibited medications for the purpose of meeting study eligibility.

6.5 Concomitant Therapy permitted

The following concomitant medications/therapy are permitted as needed and per institutional guidelines:

- supportive care medications;
- antibiotics, antifungals, anti-emetics, and other standard supportive care medications; Tavanic and Noxafil are recommended in case of ANC < 0.5 G/L;
- transfusion of blood and blood products;
- Granulocyte colony-stimulating factor (G-CSF) (may be administered when Grades 3 to 4 neutropenia occurs per clinical practice).

- Herbal supplements should be discouraged unless known not to be CYP3A active.
- If a P-glycoprotein (P-gp) inhibitor must be used, monitor closely for signs of toxicities or follow local label as applicable.
- Concomitant use of narrow therapeutic index P-gp substrates should be avoided. If a narrow therapeutic index P-gp substrate must be used, it should be taken at least 6 hours before venetoclax.
- Concomitant use of a moderate CYP3A inducer should be avoided. Alternative treatments with less CYP3A induction should be considered.
- In subjects receiving concomitant use of warfarin, closely monitor the international normalized ratio (INR).

CYP3A inhibitors and inducers should only be used when no appropriate therapeutic alternative exists.

Table 4 describes venetoclax dosage modifications based on concomitant use with a strong or moderate CYP3A inhibitor.

Table 4: Dose Modifications for Venetoclax when Co-Administered with Moderate or Strong CYP3A Inhibitors

Initial Target Venetoclax Dose*	Venetoclax Dose if Co-Administered with a Moderate CYP3A Inhibitor	Venetoclax Dose if Co-Administered with a Strong CYP3A Inhibitor
100 mg	50 mg	10 mg
200 mg	100 mg	20 mg
300 mg	150 mg	30 mg
400 mg	200 mg	50 mg

* For an initial target dose not listed in the table, reduce venetoclax dose by at least 8-fold for strong inhibitors and by at least 2-fold for moderate inhibitors. Therapy with CYP3A inhibitors are not allowed if initial target dose is less than 100 mg.

The Investigators Coordinators should be contacted if there are any questions regarding concomitant or prior therapy(ies).

Examples of clinical CYP3A inhibitors or inducers, or clinical substrates or inhibitors of transporters are provided on the Food and Drug Administration (FDA) website for Drug Development and Drug Interactions: <https://www.fda.gov/drugs/drug-interactions-labeling/drug-development-and-druginteractions-table-substrates-inhibitors-and-inducers>

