3	100 mg*	200 mg*	400 mg*

*VENETOCLAX will be given once daily orally.

**Therapy with CYP3A inhibitor are not allowed during the ramp up.

DLI will be infused every two cycles (C2, C4, C6, C8) at day 15 in absence of GVHD as follows, and at least 8 weeks after immunosuppressive therapy discontinuation. If the chimerism in > 90% recipient, DLI will not be performed.

	DLI dosage
Sibling-Id or Unrelated Donor-Id 10/10	0.5 x 10 ⁷ CD3/kg 1 x 10 ⁷ CD3/kg 0.5 x 10 ⁸ CD3/kg 1 x 10 ⁸ CD3/kg
Unrelated Donor-Id 9/10	1 x 10 ⁶ CD3/kg 5 x 10 ⁶ CD3/kg 1 x 10 ⁷ CD3/kg 0.5 x 10 ⁸ CD3/kg

Patients with Complete Remission (CR), Partial Remission (PR), marrow CR or Hematological Improvement (HI) after 8 Cycles of therapy (IWG 2006 criteria or Cheson et al. criteria for AML) continue on protocol with VENETOCLAX + AZA until 12 cycles maximum then AZA alone. Patients with no response (NR) to treatment will be withdrawn from the protocol after the last treatment Cycle.

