6.2 Dose Escalation Guidelines

Subjects in part of phase I will be enrolled into a dose-escalation study, and in 3 expansion cohorts evaluating venetoclax combined with azacitidine in subjects with MDS with myeloid neoplasms (blasts < 30%) in relapse after allo hematopoietic stem cell transplantation.

The dose escalation portion is expected to enroll approximately 9 – 18 subjects.

The first venetoclax dose-level to be evaluated in combination with azacitidine will be 100 mg QD at a dosing duration of 14 days per cycle. A cycle is defined as a time period of 28 days.

For this study, the dose limiting toxicities (DLT) observation period is defined as the first treatment cycle (Cycle 1) of venetoclax combined with azacitidine.

Dose limiting toxicities for dose escalation purposes will be determined based on adverse events that occur during the DLT observation period.

Adverse events occurring after the DLT observation period criteria will also be reviewed and may be taken into consideration for dose escalation decisions.

Any of the following events will be considered a DLT unless the event can be attributed by the investigator to a clearly identifiable cause such as underlying illness or disease progression, concurrent other illness, or concomitant medication:

- ANC $< 1 \times 10^9/L$ (Grade ≥ 3) which does not recover as defined below:
 - o Recovery is defined as an increase in ANC from nadir by $\geq 50\%$ of the reduction from baseline to nadir or any increase to an ANC of $\geq 1 \times 10^9/L$ within 42 days from Day 1 of Cycle 1
 - o Delayed recovery should only be deemed a DLT if due to treatment induced toxicity as confirmed by a bone marrow sample showing an overall bone marrow cellularity of $< 5\%$
- Grade ≥ 3 thrombocytopenia associated with clinically significant bleeding that requires transfusion of platelets over routine or baseline transfusion needs based on investigator opinion
- Grade ≥ 4 non-hematologic toxicity deemed related to venetoclax per investigator opinion.
- Grade 4 infections or complications related to infections (e.g., sepsis) should only be deemed DLTs if due to treatment-induced neutropenia as confirmed by a bone marrow sample showing an overall bone marrow cellularity of $< 5\%$

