13.13 PREMATURE TREATMENT DISCONTINUATION (Discontinuation of Individual Subjects)

Treatment will continue until the occurrence of any of the following events:

- No response after 8 cycles of therapy
- Major violation of the study protocol (violations that affect the right and safety of patients and the integrity of collected data)

- Unacceptable AE or failure to tolerate study therapy
- All grade 4 toxicities
- Persistent myelosuppression and/or cardiac toxicity
- Disease progression
- Withdrawal of consent
- Lost to follow up
- Death
- Suspected pregnancy
- Administrative decision by the investigator or the sponsor
- If the patient manifests exclusion criteria during the trial
- Subject noncompliance (deliberate protocol violations)
- A subject requires the use of a proscribed medication; the subject will need to be discontinued from treatment and end of treatment and end of study visits performed.

Where possible, patients who have discontinued their treatment prematurely will receive the same follow-up as other patients.

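### Section 6.5 recommends Noxafil at ANC below 0.5 G/L with no exception, although CYP3A inhibitors are banned during the cycle 1 ramp-up and at an initial target below 100 mg

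*Protocol*

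**What the plan says.** Section 6.5 lists therapies permitted as needed and under institutional guidelines. One bullet covers anti-infectives and adds: "Tavanic and Noxafil are recommended in case of ANC < 0.5 G/L". It names no dose level, cycle or day to which this does not apply.

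Other parts of the protocol restrict the same drug class:

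- **Ramp-up.** A footnote to the ramp-up table, in the synopsis and again in 6.1, reads "Therapy with CYP3A inhibitor are not allowed during the ramp up". It applies at every dose level and in both phases.
- **Low target dose.** The footnote to Table 4, in 6.5 itself, reads "Therapy with CYP3A inhibitors are not allowed if initial target dose is less than 100 mg". Level -1 has a target of 50 mg.
- **Last resort.** A general sentence in 6.5 reserves CYP3A inhibitors and inducers for situations with no suitable alternative.
- **Dose adjustment.** Table 4 gives a reduced venetoclax dose for use with a strong inhibitor at targets of 100, 200, 300 and 400 mg.

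Appendix 2 lists posaconazole among the strong CYP3A inhibitors. Section 6.4, which opens "The Following Medications and Therapy are not allowed during the study", names strong CYP3A inducers and grapefruit-type foods but no inhibitor drugs.

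**The concern.** The trigger for the recommendation is severe neutropenia, which is common ground for a relapsed, post-transplant MDS or AML population. Section 13.3 itself calls cytopenias part of the natural history of these diseases. A clinician treating a patient with ANC below 0.5 G/L would look under permitted therapy, find Noxafil named as recommended, and find nothing in that bullet to say that the patient may be in a period or at a dose level where it is forbidden. The list of prohibited drugs in 6.4 would not correct this.

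What is at stake is a drug interaction that the protocol itself set out to prevent, at about 20 sites. In phase I it also touches the dose-finding data. The DLT window "is defined as the first treatment cycle (Cycle 1) of venetoclax combined with azacitidine", so the ramp-up lies wholly inside it. Section 6.2 lets the investigator discount an event attributed to "disease progression, concurrent other illness, or concomitant medication", so a toxicity in such a patient may not count as a DLT, and the patient then says less about the assigned dose.

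**Working it through.** No sample size, power or error rate is involved. The check is whether one patient can satisfy both the recommendation and a ban.

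**Step 1: is Noxafil within the restricted class?** The protocol does not spell out that Noxafil is posaconazole. This is a brand-name identity and is taken as given. Appendix 2 then places it among the strong CYP3A inhibitors. Both bans are ungraded (they say CYP3A inhibitor, without strong or moderate), so they cover it.

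**Step 2: set the statements side by side for a patient with ANC below 0.5 G/L.**

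| Situation | Bullet in 6.5 | Other statement | Result |
|---|---|---|---|
| Level -1, any cycle | Noxafil recommended | Banned: 50 mg < 100 mg (Table 4 footnote) | Direct conflict |
| Levels 1 to 3, cycle 1 ramp-up | Noxafil recommended | Banned (synopsis and 6.1) | Direct conflict |
| Levels 1 to 3, after ramp-up | Noxafil recommended | Allowed at the Table 4 dose (100 to 10 mg, 200 to 20 mg, 400 to 50 mg), but reserved for lack of an alternative | No ban; tension between recommended and last resort |

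**Step 3: can the trigger occur that early?** The inclusion criteria in 6.6 set no minimum ANC. Section 6.1 starts a cycle at ANC above 1 G/L or on recovery of the baseline level, so it sets no absolute floor for a patient who is neutropenic at baseline. ANC below 0.5 G/L on cycle 1 day 1 is therefore compatible with the protocol.

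**Step 4: how far does the direct conflict reach?**

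- *Ramp-up:* the doses on days 1 and 2 of cycle 1 are below target, and the target dose starts on day 3. Every treated patient passes through it, at most 18 + 30 = 48.
- *Level -1:* no patients if 100 mg is tolerated; 3 to 6 if the level opens, assuming standard 3+3 cohorts; 30 more only if 50 mg became the phase II dose.
- *Frequency:* the documents do not say how many patients will have ANC below 0.5 G/L at these times, so no expected count can be given.

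**The case against.** The strongest reply is that the text can already be obeyed in full. A recommendation yields to a prohibition: where inhibitors are banned, a site uses another antifungal and breaks no rule. The bullet falls under a lead-in that defers to need and institutional practice. The last-resort sentence, Table 4 and its footnote follow in the same section, along with advice to contact the coordinating investigators about concomitant therapy. Section 6.4 lists what is barred throughout the study, so it is logical for conditional bans to sit elsewhere. All of this stands, and it makes the matter an unresolved contradiction in wording, not an instruction that sites must follow. It does not remove the need for a fix: the bullet names the drug as recommended and refers to none of these limits, and the ramp-up ban appears only as a table footnote in other sections.

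Four stronger readings are tempting, but the documents do not support them.

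- *That level -1 lacks a deliverable dose.* The footnote says "For an initial target dose not listed in the table, reduce venetoclax dose by at least 8-fold for strong inhibitors", and 50/8 = 6.25 mg is below the 10 mg tablet. But the same footnote then bans inhibitors below 100 mg, so no adjusted dose is due there and none is missing. Nor does the rule, written for an initial target dose, govern the day 1 and day 2 steps.
- *That exposure would rise by a known factor.* Table 4 gives dose cuts, not exposure ratios.
- *That following the bullet would end treatment under 13.13.* That rule reads "A subject requires the use of a proscribed medication; the subject will need to be discontinued from treatment". A patient who can take a different antifungal does not require the proscribed one, so this outcome is remote.
- *That exclusion 14 is inconsistent because its 3-day wash-out covers only dose-escalation cohorts.* Limiting the wash-out to those cohorts is a defensible way to protect DLT assessment, and the ramp-up ban still binds in phase II. Widening it would be a debatable change to eligibility.

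**Conclusion.** The contradiction is real and should be fixed. The 6.5 bullet recommends, without exception, a drug that the protocol forbids in two situations and elsewhere in 6.5 treats as a last resort. Because no ANC floor applies at entry, a patient can meet both conditions at once. A site relying on the bullet alone would give a prohibited interacting drug; in phase I, during the ramp-up or in cycle 1 at level -1, this would fall inside the DLT window.

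The size is modest. The direct conflict covers the first days of cycle 1, and level -1 only if that level opens. Beyond those, at 100 mg or more, Table 4 supplies a dose and what remains is the tension with the last-resort sentence. That tension is milder but can reach more patients. Nothing here alters the sample size, the two-stage rule or the error rates, and the documents support no estimate of excess toxicity.

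The conclusion rests on Noxafil being posaconazole and on the absence of an ANC requirement in the inclusion criteria and cycle-start rule as written.

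**What to change.** Replace the last part of the anti-infective bullet in 6.5 with wording such as:

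*At ANC below 0.5 G/L, Tavanic is recommended. Noxafil may be used only where no suitable alternative antifungal is available, and then with the venetoclax dose given in Table 4. No CYP3A inhibitor may be given during the cycle 1 ramp-up or to a patient whose initial target dose is below 100 mg; these patients receive an antifungal that is not a CYP3A inhibitor.*

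Keep the bans ungraded, as they are now. Limiting them to strong or moderate inhibitors would permit weak ones that the current text excludes. Sites should also note that Appendix 2 lists itraconazole, ketoconazole and voriconazole as strong inhibitors and fluconazole as moderate, so none of these can be the substitute.

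In 6.4, add a line that refers to the two conditional bans.

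The cost is a reworded bullet and one cross-reference. A few neutropenic patients would receive a different antifungal during the ramp-up or at level -1, as the bans already imply, and after the ramp-up Noxafil becomes a fallback. No extra patients, visits or procedures are needed, and eligibility does not change.

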6.6 Inclusion Criteria

Patients must meet all of the following inclusion criteria to be eligible for enrollment into the study:

1. Documented relapse of MDS or AML with marrow blasts < 30% (with WBC < 15000/mm³), after allo-SCT.
Relapse of MDS or AML is defined as:
 - ✓ Return to pretreatment bone marrow blast percentage
 - ✓ Decrement of at least 50% from maximum remission
2. Age ≥ 18 years.
3. Eastern Cooperative Oncology Group (ECOG) performance status ≤ 2.
4. Patient must have adequate organ function as indicated by the following laboratory values:

System	Laboratory Value
Renal	
Serum creatinine	< 2 mg/dl
or calculated creatinine clearance ^a	OR ≥ 30 mL/min for patients with creatinine levels > 1.5 x institutional ULN
Hepatic	
Serum total bilirubin	≤ 2.5 x ULN OR direct bilirubin ≤ ULN for patients with total bilirubin levels ≥ 2 mg/dL.
AST (SGOT) and ALT (SGPT)	≤ 2.5 x ULN
Alkaline Phosphatase	≤ 5 x ULN If > 2.5 x ULN, then liver fraction should be ≤ 2.5 x ULN
^a Creatinine clearance should be calculated per institutional standard.	

5. Patient not refractory to platelet transfusions.
6. Female subject of childbearing potential must practice at least one protocol specified method of birth control (**see appendix 3**), starting on Study Day 1 through at least 30 days after the last dose of venetoclax or 3 months after the last dose of azacitidine.
Not being of childbearing potential is defined as:
 - Age > 55 years with no menses for 12 or more months without an alternative medical cause, or
 - Age ≤ 55 years with no menses for 12 or more months without an alternative medical cause AND an FSH level > 40 IU/L, or
 - Permanent surgical sterility (bilateral oophorectomy, bilateral salpingectomy or hysterectomy).
7. Female subjects of childbearing potential must have negative results for pregnancy test performed:
 - At Screening with a serum sample obtained within 14 days prior to the first study drug administration, and
 - Prior to dosing with urine sample obtained on Cycle 1 Day 1, if it has been > 7 days since obtaining the serum pregnancy test results.

Female subjects who are not of childbearing potential at Screening do not require pregnancy testing.

8. Male subjects sexually active with female partner(s) of childbearing potential, must agree from first dose of study drug(s) through at least 30 days after the last dose of venetoclax or 3 months after the last dose of azacitidine, whichever is later, to practice the protocol specified contraception (**see appendix 3**).
9. Patient is available for periodic blood sampling, study related assessments, and appropriate clinical management at the treating institution for the duration of the study.
10. Patient has the ability to understand and willingness to sign an informed consent form indicating the investigational nature of the study.
11. Patient is able to swallow capsules.

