5 STUDY ENDPOINTS

5.1 Primary endpoint

Phase I: To determine toxicity profile and safety of the combination

Phase II: Overall hematological response rate of venetoclax in combination with AZA/DLI

Response assessment will be performed according to modified IWG 2006 criteria for MDS and according European LeukemiaNet criteria for AML.

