9 CRITERIA FOR MEASUREMENT OF STUDY ENDPOINTS

9.1 Efficacy Outcome Measures

Primary Endpoint:

For MDS patients:

Overall response rate (ORR), defined as the proportion of patients who achieve a CR or PR per proposal for modification of the International Working Group (IWG) criteria for MDS, 2006 (Appendix 11):

1. CR is defined as bone marrow blasts $\leq 5\%$, without persistent dysplasia will be noted with normal maturation of all cell lines peripheral blood: Hgb ≥ 11 g/dL platelets $\geq 100 \times 10^9/L$, ANC $\geq 1.0 \times 10^9/L$, blasts 0%.
2. PR is defined as all CR criteria if abnormal before treatment except for bone marrow blasts decreased by $\geq 50\%$ over pretreatment but still $> 5\%$ cellularity.

For AML patients:

CR Rate, defined as the proportion of patients who achieve a CR per the ELN2017 criteria: CR is defined as BM blasts $< 5\%$, absence of circulating blasts and blasts with Auer rods, absence of extramedullary disease, ANC $\geq 1.0 \times 10^9/L$ (1,000/ μ L); platelet count $\geq 100 \times 10^9/L$ (100,000/ μ L).

Secondary Endpoints:

For MDS patients:

1. Overall improvement rate (OIR), defined as the proportion of patients reaching a CR, Marrow CR, PR, or hematologic improvement (HI) per proposal for modification of the IWG criteria for MDS, 2006 (Appendix 11). Marrow CR is defined as bone marrow blasts $\leq 5\%$ and decreased by 50% over pretreatment. Peripheral blood: if HI responses, they will be noted in addition to marrow CR. HI is defined as:
 - a. Erythroid response (pretreatment, < 11 g/dL) is defined as Hgb increase by ≥ 1.5 g/dL. Relevant reduction of units of red blood cells (RBC) transfusions by an absolute number of at least 4 RBC transfusions/8 weeks, compared with the pretreatment transfusion number in the previous 8 weeks. Only RBC transfusions given for a Hgb of ≤ 9.0 g/dL will count in the RBC transfusion response evaluation.
 - b. Platelet response (pretreatment $< 100 \times 10^9/L$) is defined as absolute increase of $\geq 30 \times 10^9/L$ for patients starting with $> 20 \times 10^9/L$ platelets, and an increase from $< 20 \times 10^9/L$ to $> 20 \times 10^9/L$ and by at least 100%.
 - c. Neutrophil response (pretreatment, $< 1.0 \times 10^9/L$) is defined as at least 100% increase and an absolute increase $> 0.5 \times 10^9/L$

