10.2 Efficacy Endpoints

Efficacy will be evaluated by the investigator according to the 2006 IWG response criteria in MDS and for AML according to AML in Adults: 2017 ELN Recommendations from an International Expert Panel Revised (Döhner et al., 2017).

The analyses for efficacy will be performed for the following endpoints.

Overall Response Rate

The proportion of subjects with overall response ($OR = CR + mCR + PR + HI$) will be calculated. The 95% confidence interval for OR rate based on binomial distribution will be constructed.

Complete Remission Rate

The proportion of subjects with complete remission (CR) will be calculated. The 95% confidence interval for CR rate based on binomial distribution will be constructed.

Marrow Complete Remission Rate

The proportion of subjects with mCR with or without hematological improvement will be calculated. The 95% confidence interval for mCR rate based on binomial distribution will be constructed.

Partial remission (PR)

The proportion of subjects with PR with or without hematological improvement will be calculated. The 95% confidence interval for PR rate based on binomial distribution will be constructed.

Hematologic Improvement

The proportion of subjects with HI (erythroid/platelet/neutrophil responses) will be calculated. The 95% confidence interval for the rate of HI based on binomial distribution will be constructed.

Time to AML Transformation

Time to AML transformation will be defined as the number of days from the date of the first dose of study drug to the date of documented AML transformation. AML transformation will be defined as the presence of blast count $\geq 20\%$ in either the peripheral blood or bone marrow. Time to AML transformation will be summarized as median (range). Subjects who do not show transformation to AML will not be included in the analysis.

Duration of Response

Duration of response (DOR) will be defined as the number of days from the date of first response (CR, mCR, PR or HI) to the earliest documentation of progressive disease (PD). Duration of response will be analyzed by Kaplan-Meier methodology. Median DOR will be calculated and 95% confidence interval for median DOR will be presented.

If the response is still ongoing at the time of analysis, the subject's data will be censored at the date of the subject's last available disease assessment. For subjects who never experience a response, the subject's data will not be included in the analysis.

Overall Survival

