24.9 Appendix 9: Groups according to FAB-classification

Subtype	Percentage of blasts blood bone marrow	Further changes
Refractory anemia (RA)	≤ 1 % < 5 %	
Refractory anemia with ringed sideroblasts (RARS)	≤ 1 % < 5 %	> 15 % ringed sideroblasts within erythropoiesis
Refractory anemia with excess of blasts (RAEB)	< 5 % 5-20 %	
RAEB in transformation (RAEB-T)	> 5 % 20-30 %	facultative Auer rods
Chronic myelomonocytic leukemia (CMML)	< 5 % 0-20 %	peripheral monocytosis (> 1000/μl)

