24.10 Appendix 10: Groups according to WHO-classification 2016

Subtype	Dysplastic lines	Cytopenias	Ring sideroblasts (% of erythroid cells)	Blasts in BM and PB	Karyotype (conventional banding)
MDS-SLD	1	1 or 2	<15% / <5 % ²	BM <5%, PB <1% no Auer rods	All, except del(5q) ± 1 other non-chr 7 abnormality
MDS-MLD	2 or 3	1-3	<15% / <5 % ²	BM <5%, PB <1% no Auer rods	All, except del(5q) ± 1 other non-chr 7 abnormality
MDS-RS					
MDS-RS-SLD	1	1 or 2	<15% / <5 % ²	BM <5%, PB <1% no Auer rods	All, except del(5q) ± 1 other non-chr 7 abnormality
MDS-RS-MLD	2 or 3	1-3	<15% / <5 % ²	BM <5%, PB <1% no Auer rods	All, except del(5q) ± 1 other non-chr 7 abnormality
MDS with del(5q)	1-3	1 or 2	not relevant	BM <5%, PB <1% no Auer rods	Isolated del(5q) or with 1 other non-chr 7 abnormality
MDS-EB					
MDS-EB1	0-3	1-3	not relevant	BM 5-9% or PB 2-4% no Auer rods	not relevant
MDS-EB2	0-3	1-3	not relevant	BM 10-19% or PB 5-19% or Auer rods	not relevant
MDS-U (unclassifiable)					
with 1% blood blasts	1-3	1-3	not relevant	BM <5%, PB =1% no Auer rods	not relevant
with single lineage dysplasia and pancytopenia	1	3	not relevant	BM <5%, PB <1% no Auer rods	not relevant
based on defining cytogenetic abnormality	0	1-3	<15% ⁴	BM <5%, PB <1% no Auer rods	MDS-defining abnormality

1 cytopenias defined as hemoglobin < 100 g/L, Platelets < 100 x 10⁹/L, ANC <1.8 x 10⁹/L

2 if SF3B1 has a mutation

3 1 % peripheral blasts have to be judged at 2 different times

4 Cases with ≥ 15% of ring sideroblasts have (per definition) significant dyserythropoiesis and are therefore MDS-RS-SLD

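### The phase II primary endpoint depends on an MDS or AML label that no rule assigns, and the protocol is inconsistent about marrow blasts of 20-29%

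*Protocol*

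**What the plan says.** Section 6.6, criterion 1, admits "Documented relapse of MDS or AML with marrow blasts < 30" per cent after allogeneic transplant and gives one definition of relapse for both diseases. Section 5.1 selects the response criteria by disease: "Response assessment will be performed according to modified IWG 2006 criteria for MDS and according European LeukemiaNet criteria for AML".

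Section 9.1 makes the primary endpoint itself depend on the disease. For MDS it is "Overall response rate (ORR), defined as the proportion of patients who achieve a CR or PR". For AML it is "CR Rate, defined as the proportion of patients who achieve a CR per the ELN2017 criteria".

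No section states whether the label comes from the diagnosis before transplant, from the marrow at relapse, or from a named classification. The places that deal with blasts of 20-29% differ:

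- **On the MDS side:** Appendix 9 (FAB) lists RAEB-T at 20-30% marrow blasts, Appendix 11 (section 24.11.7) has an MDS progression stratum for 20-30%, and the IPSS table in Appendix 7 scores 21-30%.
- **Outside MDS:** the highest MDS category in Appendix 10 (WHO 2016) is "BM 10-19% or PB 5-19% or Auer rods". Section 10.2 says "AML transformation will be defined as the presence of blast count" of 20% or more in blood or marrow.

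Section 10.2 also gives an overall response of CR + mCR + PR + HI with no split by disease, which does not match section 9.1.

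**The concern.** The label decides whether a PR counts towards the primary endpoint, so it should be fixed before treatment by a stated rule. An eligible patient with 20-29% blasts at relapse can be placed on either side from the protocol's own tables. The trial is open-label and single-arm, and the investigator assesses efficacy. Without a rule, two sites could score the same course differently, and nothing in the protocol prevents the label from being settled after the marrow result is known.

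A second consequence concerns time to AML transformation, a secondary endpoint for MDS patients. A patient labelled MDS who enters with 20-29% blasts already meets the section 10.2 definition at baseline.

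**Working it through.** **1. One patient, two labels.** Baseline marrow blasts are 24%, later 7%, with CR-level blood counts and no circulating blasts.

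- Relative fall: (24 − 7)/24 = 71%.
- Appendix 11, PR: fall of at least 50% and still above 5%. Met.
- Appendix 12, PR: marrow blasts 5-25%, fall of at least 50%, haematologic criteria of CR. Met.
- Section 9.1: success if MDS, failure if AML.

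The label can also work the other way. MDS CR in section 9.1 requires haemoglobin of at least 11 g/dL, and AML CR has no haemoglobin criterion. With 3% blasts, ANC 1.2, platelets 120 and haemoglobin 9.5 g/dL, the patient is an AML success but neither CR nor PR as MDS.

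Progression differs too where section 10.2 refers to Appendices 11 and 12. A rise from 22% to 34% is +55% to above 30%, which is progression in Appendix 11. It is 12 points, short of the 15-point minimum for the marrow criterion in Appendix 12.

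**2. The stated design.** Inputs from section 3: continue at 4 or more responses of 14, success at 13 or more of 30, null rate 30%, target 50%, alpha 0.05, beta 0.20.

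P(success | p) = Σ over x = 4 to 14 of P(X₁ = x) · P(X₂ ≥ 13 − x), with X₁ ~ Bin(14, p) and X₂ ~ Bin(16, p).

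- p = 0.50: 0.814. The stated power is reproduced.
- p = 0.30: 0.083, above the stated 0.05. That discrepancy is a separate matter and is not part of this point.

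**3. How far labelling moves the null.** Section 2 gives 7 CR and 2 PR among the responses behind the 30% rate, that is, 23% and 7% of 30 patients. If a share q of patients is labelled AML, their PRs do not count, so the null rate is p₀ = 0.30 − q × 2/30. Let a be the ambiguous share and split the rest evenly between AML and MDS. Then q = (1 + a)/2 if all ambiguous patients are labelled AML, and (1 − a)/2 if all are labelled MDS. The protocol does not give a, so a range is assumed.

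| a | p₀, ambiguous all AML | P(success) | p₀, ambiguous all MDS | P(success) |
|---|---|---|---|---|
| 10% | 0.263 | 3.2% | 0.270 | 3.9% |
| 20% | 0.260 | 2.9% | 0.273 | 4.2% |
| 30% | 0.257 | 2.6% | 0.277 | 4.6% |

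The ratio within a row runs from 3.9/3.2 = 1.2 to 4.6/2.6 = 1.8. The extremes, with every patient AML (p₀ = 7/30) or every patient MDS (p₀ = 0.30), give 1.2% and 8.3%.

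**4. Individual patients.** At the historical PR rate, the expected number of PRs from the ambiguous band among 30 patients is 30 × a × 2/30 = 2a, that is, 0.2 to 0.6. The chance of two or more, from Bin(30, a × 2/30), is 2% at a = 10% and 12% at a = 30%. One relabelled PR alters the decision only at 13/30 against 12/30, or at 4/14 against 3/14.

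**The case against.** Four objections carry weight.

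**Prior AML relapsing at 5-19% blasts.** A reader might infer that these patients are equally unlabelled. The documents do not support that. Criterion 1 requires a documented relapse, which is of a disease already diagnosed, and Appendix 12 defines haematologic relapse of AML as marrow blasts of 5% or more. Such a patient reads naturally as relapsed AML, and nothing reclassifies the case by the relapse marrow. The gap is the 20-29% band, mainly in patients transplanted for MDS.

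**The appendices are reference tables.** Appendices 7, 9 and 10 reproduce external systems, and the body does not use them to assign disease. They are therefore not competing assignment rules. However, Appendix 11 is invoked for response and progression and keeps a 20-30% stratum, while section 10.2 uses 20% as the AML limit. That inconsistency stands, and so does the absence of any rule.

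**Section 10.2 counts PR for everyone.** Under its undivided definition, the worked PR is a response with either label. The success or failure split holds only under section 9.1. This is a further conflict to resolve and does not supply a labelling rule.

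**The data precede treatment.** Medical history and marrow are collected at screening, and a labelling convention might sit in an SAP that is not shown. But the label selects the primary endpoint, and both that endpoint and the inconsistent thresholds are in the protocol. Nothing in the documents shows that relabelling after the result is intended or likely. The point is only that the protocol does not rule it out.

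**Conclusion.** The point holds for marrow blasts of 20-29%. The protocol makes its primary endpoint depend on a label, gives no rule for it, and is inconsistent about this band. As section 9.1 stands, a PR there is a success under MDS and a failure under AML, and a patient labelled MDS meets the transformation definition at entry.

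The effect on the operating characteristics is modest: a 1.2- to 1.8-fold range in false-positive probability for an ambiguous share of 10-30%. This rests on that assumed share, an even split of the remaining patients, and the historical 7 CR and 2 PR of 30 applying under both labels.

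A reader might infer from 1.2% against 8.3% that labelling alone moves the error about 7-fold. That comparison needs every patient to change label, so it is only an outer bound. Nor is a shift from 11 to 13 responders a typical effect, because both PRs would have to fall in the ambiguous band. Likewise, time to AML transformation fails only for MDS-labelled patients who enter at 20% or more, not for the endpoint as a whole.

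**What to change.** - **Labelling rule:** state in section 6.6 one rule for the disease category. For example: AML if AML was documented before transplant or relapse blasts are 20% or more, otherwise MDS. Any single pre-specified rule closes the gap.
- **Lock:** record the category in the eCRF before Cycle 1 Day 1 and use it for all response and progression criteria.
- **Appendices:** reconcile the 20-30% entries in Appendices 9 and 11 with the rule.
- **Transformation:** restrict time to AML transformation to MDS patients with less than 20% blasts at baseline.
- **Response definition:** reconcile the primary response of section 9.1 with the CR + mCR + PR + HI of section 10.2. Without this, a locked label still leaves two answers for the same PR.

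The cost is one sentence and one eCRF field for the label, plus the wording changes above. The data are already collected at screening. Under the example rule, a few PRs in the 20-29% band may count as non-responses, so the observed rate could be slightly lower.
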